Research question and objectives	
1. Estimate the annual incidence of HIV diagnoses among all people without HIV in OPERA
a. Among people with an incident HIV diagnosis, characterize history of PrEP use2. Describe the demographic and clinical characteristics of people who initiate oral and LA PrEP3. Estimate the frequency and rate of incident HIV diagnoses following index oral PrEP or LA PrEP initiation among people who initiate a PrEP regimen4. Evaluate PrEP coverage within 12-months following index oral PrEP or LA PrEP initiation among people who initiate a PrEP regimen5. Assess HIV testing and STI screening patterns at index oral or LA PrEP initiation and within 12-months following index PrEP initiation among people who initiate a PrEP regimen6. Describe demographic and clinical characteristics, HIV testing and diagnoses, as well as STI screening and diagnoses over a 12-month period of follow-up among people who are not on PrEP but could benefit from PrEP
Country(-ies) of study	United States
Author	PPD

MARKETING AUTHORISATION HOLDER(S)

Protocol for Non-Interventional Studies PASS Studies and Non-PASS Studies (4.0) March 2024
Template Doc ID: TMF-15706807
Parent Doc ID: VQD-SOP-066694

Marketing authorisation holder(s)	ViiV Healthcare Company [name]
MAH contact person	N/A

TABLE OF CONTENTS

	PAGE
TITLE PAGE.....	3
LIST OF ABBREVIATIONS	9
1. RESPONSIBLE PARTIES	11
1.1. Sponsor Signatory.....	12
1.2. Investigator Protocol Agreement Page	13
2. SYNOPSIS.....	14
3. AMENDMENTS AND UPDATES	17
4. MILESTONES	18
5. RATIONALE AND BACKGROUND.....	19
6. RESEARCH QUESTION AND OBJECTIVE(S).....	20
7. RESEARCH METHODS	20
7.1. Study Design	20
7.2. Study Population and Setting	22
7.2.1. Inclusion Criteria	22
7.3. Variables.....	23
7.3.1. Exposure definitions.....	24
7.3.2. Outcome definitions.....	24
7.3.3. Confounders and effect modifiers	29
7.4. Data sources.....	29
7.5. Study size	30
7.6. Data management.....	31
7.7. Data analysis	32
7.7.1. Primary analysis.....	32
7.7.1.1. Main Analytical approach	32
7.7.1.2. Data handling conventions	33
7.8. Quality control and Quality Assurance.....	33
7.9. Limitations of the research methods.....	36
7.9.1. Study closure/uninterpretability of results.....	36
8. PROTECTION OF HUMAN SUBJECTS	36
8.1. Ethical approval and subject consent	36
8.2. Subject confidentiality.....	37

12. REFERENCES39

ANNEX 1 TABLES41

LIST OF ABBREVIATIONS

AE	Adverse Event
CAB	Cabotegravir
CI	Confidence intervals
CMS	Centers for Medicare & Medicaid Services
EHR	Electronic health record
FTC	Emtricitabine
FU	Follow-up
GSK	GlaxoSmithKline
HBV	Hepatitis B virus
HCP	Healthcare provider
HCV	Hepatitis C virus
HPV	Human papilloma virus
HSV-2	Herpes Simplex-2
LA	Long acting
NA	Not applicable
Obj	Objective
PHI	Protected health information
PrEP	Pre-exposure prophylaxis
STI	Sexually transmitted infection
TAF	Tenofovir alafenamide
TDF	Tenofovir disoproxil fumarate
US	United States

TRADEMARK INFORMATION

Trademarks of the <<GSK\ViiV>> group of companies
APRETUDE

Trademarks not owned by the <<GSK\ViiV>> group of companies
OPERA

2. SYNOPSIS

Title Frequency of HIV diagnoses among people using oral and LA PrEP

Rationale and Background

In the US, out of approximately 1.2 million people who could benefit from pre-exposure prophylaxis (PrEP), it was estimated that approximately 30% had received a PrEP prescription in 2021. Oral PrEP has been shown to be an effective form of HIV prevention. When taken as prescribed, daily oral PrEP reduces the risk of HIV diagnosis by 99% compared to placebo or those who do not use PrEP among men who have sex with men. Tenofovir disoproxil fumarate (TDF)/emtricitabine (FTC) was approved for PrEP on 16JUL2012 and tenofovir alafenamide (TAF)/FTC was approved on 3OCT2019. The effectiveness of oral PrEP depends on the level of adherence to the daily pill regimen. Cabotegravir long-acting injectable (CAB LA) PrEP was approved on 20DEC2021 and has been shown to have superior efficacy compared to daily oral TDF/FTC. The CDC guidelines for PrEP indicate that HIV testing is required before PrEP initiation and recommended every 3 months (oral PrEP) or 2 months (CAB LA PrEP). The guidelines also recommend regular screening for syphilis, gonorrhea and chlamydia for PrEP users. It is important to understand patterns of PrEP use among people who acquire HIV to improve public health and clinical practice. This study will also provide crucial real-world evidence on HIV acquisition on PrEP, PrEP coverage, HIV testing and STI screening in individuals receiving either oral or LA PrEP.

Research Question and Objective(s)

Analyses to meet the study objectives below will be conducted twice during the study period. Analysis #1 will include data from 01JAN2021-31DEC2023 (Obj. 1) and from 21DEC2021-30JUN2024 (Obj. 2-6). Analysis #2 will be a repeat of Analysis #1 with data from 1JAN2021-31DEC2024 (Obj. 1) and from 21DEC2021-30JUN2025 (Obj. 2-6).

1. Estimate the annual incidence of HIV diagnoses among all people without HIV in OPERA
 - a. Among people with an incident HIV diagnosis, characterize history of PrEP use
2. Describe the demographic and clinical characteristics of people who initiate oral and LA PrEP
3. Estimate the frequency and rate of incident HIV diagnoses following index oral PrEP or LA PrEP initiation among people who initiate a PrEP regimen
4. Evaluate PrEP coverage within 12-months following index oral PrEP or LA PrEP initiation among people who initiate a PrEP regimen
5. Assess HIV testing and STI screening patterns at index oral or LA PrEP initiation and within 12-months following index PrEP initiation among people who initiate a PrEP regimen
6. Describe demographic and clinical characteristics, HIV testing and diagnoses, as well as STI screening and diagnoses over a 12-month period of follow-up among people who are not on PrEP but could benefit from PrEP

Study Design

Design: Cohort study using secondary data from electronic medical records in the OPERA cohort.

Exposure groups: Oral PrEP, LA PrEP

Duration of study:

- Analysis #1: 2021 to 2023 (Obj 1-1a); 21DEC2021 to 30JUN2024 (Obj 2-6)
- Analysis #2: 2021 to 2024 (Obj 1-1a); 21DEC2021 to 30JUN2025 (Obj 2-6)

Population

(Obj 1) People in OPERA aged ≥ 18 years with ≥ 1 clinical encounter during the calendar year of interest and no evidence of prior HIV diagnosis.

(Obj 1a) People with an incident HIV diagnosis identified in Obj 1.

(Obj 2-5) People without HIV in OPERA aged ≥ 18 years who initiated any new PrEP formulation during the study period with or without prior PrEP use.

(Obj 6) People without HIV in OPERA aged ≥ 18 years who could benefit from PrEP and are not on PrEP

Variables

Exposures:

- PrEP use (never, use within ≤ 12 months before diagnosis, use > 12 months before diagnosis)
- Time-updated PrEP type (oral or LA)

Outcomes:

- Incident HIV diagnosis: New HIV diagnosis *and/or* detectable HIV RNA *and/or* positive antigen/antibody test
- PrEP coverage: Proportion of days of access to oral PrEP or proportion of days of coverage by CAB LA
- HIV testing/STI screening: frequency and type of tests performed

Data Sources

OPERA cohort, a multi-site observational database built from the complete patient health records managed in electronic health record (EHR) systems throughout the US.

Study Size

Between 21DEC2021 and 30JUN2023 (Analysis # 1 inclusion period), 22,234 adults without HIV started a new PrEP formulation in OPERA. The first formulation used during the study period was TAF/FTC oral (n=12,110, 54%), TDF/FTC oral (n=9,740, 44%), or CAB LA (n=384, 2%). An additional 292 individuals switched to CAB LA PrEP later during the study period, for a total of 767 people receiving CAB LA injections during the Analysis #1 inclusion period.

Protocol for Non-Interventional Studies PASS Studies and Non-PASS Studies (4.0) March 2024

Template Doc ID: TMF-15706807

Parent Doc ID: VQD-SOP-066694

Data Analysis

(Obj 1) For each calendar year (2021-2024), the number and percentage of incident HIV diagnoses will be reported out of all individuals receiving care at an OPERA clinic.

(Obj 1a) Among people with incident HIV diagnoses, PrEP use (never, use within ≤ 12 months before diagnosis, use > 12 months before diagnosis) and PrEP characteristics will be described.

(Obj 2) Baseline demographic and clinical characteristics will be described for people initiating a PrEP regimen, by regimen type (oral or LA).

(Obj 3) The number, percentage, and incidence rate (per 100 person-years) of HIV diagnoses within 12-months following index oral or LA PrEP initiation and through study end will be described by regimen type (time-updated, oral or LA).

(Obj 4) The percentage of days with access to oral PrEP and the percentage of days with coverage by CAB LA PrEP will be described within 12-months following index PrEP initiation.

(Obj 5) The frequency, rate (per 100 person-years), and characteristics of HIV testing and STI screening at index oral or LA PrEP initiation and within 12-months following index PrEP initiation will be described by PrEP regimen type (oral or LA), type of healthcare provider (MD or DO, physician associate, nurse practitioner, other/unknown) and clinic type (healthcare center, wellness center, other).

(Obj 6) Baseline demographic and clinical characteristics will be described for all people who could benefit from PrEP but are not on PrEP. The frequency and rate (per 100 person-years) of HIV testing and diagnosis as well as STI screening and diagnosis will be estimates over a 12-month period of follow-up among people who could benefit from PrEP but are not on PrEP. Characteristics of the tests conducted will be described by type of healthcare provider (MD or DO, physician associate, nurse practitioner, other/unknown) and clinic type (healthcare center, wellness center, other).

3. AMENDMENTS AND UPDATES

Amendment or update no	Date	Section of study protocol	Amendment or update	Reason
<<1>>	<< Date (DD Month YYYY)>>	<<Text >>	<<Text>>	<<Text>>
<<2>>	<< Date (DD Month YYYY)>>	<<Text>>	<<Text>>	<<Text>>
<<n>>	<< Date (DD Month YYYY)>>	<<Text >>	<<Text>>	<<Text>>

4. MILESTONES

Milestone	Planned date
Draft protocol	July 2024
Protocol Review Committee	July 2024
Final Protocol	Effective Date
Analysis #1 results	October 2024
Analysis #2 results	September 2025
Final Study Report (Analysis #1-2 results)	October 2025

5. RATIONALE AND BACKGROUND

In the US, the yearly number of HIV diagnoses declined on average by 2-3% between 2016 and 2019, with a total of 36,585 diagnoses in 2019. In 2020, a 17% decline in HIV diagnosis were observed, down to 30,403 diagnoses as a result of disruptions in testing services during the COVID-19 pandemic.¹ The number of new HIV diagnoses rebounded to 36,136 in 2021 and 37,981 in 2022.² Of approximately 1.2 million people in the US who could benefit from pre-exposure prophylaxis (PrEP) in 2022, it was estimated that only around 36% had received a PrEP prescription (due to limitations with the numerator and denominator, PrEP coverage reporting by the CDC has been paused for one year)^{3,4}

Oral PrEP was introduced as a form of HIV prevention when the single tablet combination of tenofovir disoproxil fumarate (TDF) and emtricitabine (FTC) was approved by the FDA on 16JUL2012. A meta-analysis of 14 clinical trials, open-label extension studies or demonstration studies found an incidence of HIV of 1.1% (95% CI: 0.6, 2.0). Compared to the non-PrEP control groups, the relative risk for incident HIV was 0.24 (95% CI: 0.11, 0.54).⁵ Of note, higher blood levels of TDF/FTC (indicating better adherence) were correlated with a lower incidence of HIV.⁵ The second oral PrEP option, a single tablet combination of tenofovir alafenamide (TAF) and FTC was approved on 30OCT2019. TAF/FTC was demonstrated to be non-inferior to TDF/FTC in men in a clinical trial.⁶ When taken as prescribed, daily oral PrEP reduces the risk of HIV diagnosis by 99% compared to placebo or those who do not use PrEP among men who have sex with men.⁷ Of note, the efficacy of oral PrEP is highly correlated with adherence.^{5,8} Cabotegravir long-acting injectable (CAB LA) PrEP was approved for the prevention of HIV by the FDA on 20DEC2021.⁹ Clinical trials have demonstrated the superior efficacy of CAB LA PrEP over daily oral TDF/FTC for HIV prevention.^{10,11} CAB LA PrEP consists of intramuscular injections given by a healthcare professional and is considered directly observed prevention.

The CDC guidelines for PrEP indicate that HIV testing is required before PrEP initiation to confirm the person does not have HIV. When oral PrEP is used, it is recommended to repeat HIV testing every 3 months before refilling or reissuing the PrEP prescription. When CAB LA PrEP is used, HIV testing is recommended every 2 months, at the time the injection is administered.⁷ HIV testing for PrEP should consist of a laboratory antigen/antibody test or a point-of-care fingerstick antigen/antibody test; rapid tests using oral fluids lack the sensitivity to detect recent infection.⁷

PrEP clinical care represents an opportunity to provide reproductive & sexual health-related services, such as STI screening. The CDC guidelines for PrEP recommends regular screening for syphilis, gonorrhea and chlamydia.⁷ A systematic review of 91 PrEP programs implementing STI testing services in 32 countries found that only 70% of PrEP programs conducted STI screening before PrEP start, and 70% screened for STI every 3 months. However, in high-income countries, screening was high for gonorrhea (92%), chlamydia (92%) and syphilis (87%), but low for hepatitis A (18%) and hepatitis C (43%).¹² In the US, a survey study found that among 809 current or former PrEP users, 91% reported receiving HIV testing at every PrEP care visit. As for STI screening, a blood sample, urine/urethral swab or a rectal swab was collected at every PrEP care visit in 67%, 57% and 36% of participants, respectively.¹³

It is important to understand patterns of PrEP use among people with incident HIV diagnosis to

improve public health and clinical practice. This study will also provide crucial real-world evidence on incident HIV diagnoses on PrEP, PrEP coverage, HIV testing and STI screening in individuals on either oral or LA PrEP.

6. RESEARCH QUESTION AND OBJECTIVE(S)

Primary Objectives

1. Estimate the annual incidence of HIV diagnoses among all people without HIV in OPERA
 - a. Among people with an incident HIV diagnosis, characterize history of PrEP use
2. Describe the demographic and clinical characteristics of people who initiate an oral or LA PrEP regimen
3. Estimate the frequency and rate of incident HIV diagnoses following index oral PrEP or LA PrEP initiation among people who initiate a PrEP regimen
4. Evaluate PrEP coverage within 12-months following index oral PrEP or LA PrEP initiation among people who initiate a PrEP regimen
5. Assess HIV testing and STI screening patterns at index oral or LA PrEP initiation and within 12-months following PrEP initiation, as well as the frequency and rate of STI diagnoses among people who initiate a PrEP regimen
6. Describe demographic and clinical characteristics, HIV testing, HIV diagnoses, STI screening and STI diagnoses over a 12-month period of follow-up among people who are not on PrEP but could benefit from PrEP

7. RESEARCH METHODS

7.1. Study Design

A cohort study using secondary data from the OPERA[®] (Observational Pharmacology Epidemiology Research & Analysis) cohort will be used to answer the study objectives. OPERA is a multi-site observational database collecting data prospectively from the complete electronic health records (EHR) from clinical care throughout the US.

[figure not shown]
Analyses to meet the study objectives will be conducted twice during the study period. Analysis #1 will include data from 01JAN2021-31DEC2023 (Obj. 1-1a) and from 21DEC2021 to 30JUN2024 (Obj 2-6). Analysis #2 will be a repeat of Analysis #1 with data from 1JAN2021-31DEC2024 (Obj. 1-1a) and from 21DEC2021 to 30JUN2025 (Obj 2-6). A

summary of the study design is provided in Table 1 (exposure groups, index date, censoring criteria, endpoints) and in Figure 1 (timeline).

Table 1. Summary of study design

		Analysis #1	Analysis #2
Obj 1 Among all people without HIV in OPERA	Exposure groups	Calendar years	Calendar years
	Index date	NA	NA
	Censoring criteria	NA	NA
	Endpoints	HIV diagnosis	HIV diagnosis
Obj 1a Among people with a new HIV diagnosis	Exposure groups	PrEP use (never, use within ≤12 months before diagnosis, use >12 months before diagnosis)	PrEP use (never, use within ≤12 months before diagnosis, use >12 months before diagnosis)
	Index date	Date of HIV diagnosis	Date of HIV diagnosis
	Censoring criteria	NA	NA
	Endpoints	NA	NA
Obj 2-5 Among PrEP users	Exposure groups	Oral PrEP, CAB LA PrEP	Oral PrEP, CAB LA PrEP
	Index date	Start of first PrEP regimen during the study period	Start of first PrEP regimen during the study period
	Censoring criteria	Death, loss to follow-up (12 months after last clinical contact), study end (30JUN2024), 12 months after index date	Death, loss to follow-up (12 months after last clinical contact), study end (30JUN2025), 12 months after index date
	Endpoints	HIV diagnosis, PrEP coverage, HIV testing, STI screening, STI diagnoses	HIV diagnosis, PrEP coverage, HIV testing, STI screening, STI diagnoses
Obj 6 Among people who could benefit from PrEP	Exposure groups	NA	NA
	Index date	First OPERA visit with indication for PrEP during study period	First OPERA visit with indication for PrEP during study period
	Censoring criteria	Death, loss to follow-up, study end (30JUN2024), 12 months after index date, PrEP initiation	Death, loss to follow-up, study end (30JUN2025), 12 months after index date, PrEP initiation
	Endpoints	HIV testing, HIV diagnoses, STI screening, STI diagnoses	HIV testing, HIV diagnoses, STI screening, STI diagnoses

Figure 1. Study timeline

^a Inclusion dates: 1JAN202X to 31DEC202X of each year

^b Inclusion dates: 21DEC2021 to 30JUN2023, with potential follow-up through 30JUN2024

^c Inclusion dates: 21DEC2021 to 31JUN2024, with potential follow-up through 30JUN2025

7.2. Study Population and Setting

7.2.1. Inclusion Criteria

People without HIV in OPERA (Obj 1)

- i. ≥ 1 clinical encounter in OPERA during the calendar year of interest
- ii. ≥ 18 years old at the first clinical encounter during the calendar year of interest
- iii. No evidence of prior HIV diagnosis

People with a new HIV diagnosis (Obj 1.a)

- i. Incident HIV diagnosis (new HIV diagnosis/positive HIV test/detectable HIV RNA viral load) identified in Obj 1

PrEP users (Obj 2-5)

- i. HIV-negative
- ii. ≥ 18 years of age
- iii. Started any new PrEP formulation
 - Analysis #1: between 21DEC2021 and 30JUN2023
 - Analysis #2: between 21DEC2021 and 30JUN2024
- iv. With or without prior PrEP use (a different formulation or a gap ≥ 61 days without any PrEP immediately prior to the index PrEP; the same formulation may have been used ≥ 61 days before starting the index PrEP)

People who could benefit from PrEP (Obj 6)

- i. HIV-negative
- ii. ≥ 18 years of age

- iii. ≥ 1 clinical encounter in OPERA during the inclusion period
 - Analysis #1: between 21DEC2021 and 30JUN2023
 - Analysis #2: between 21DEC2021 and 30JUN2024
- iv. Any of the following indications for PrEP¹¹:
 - Bacterial STI in past 12 monthsⁱ (gonorrhea, syphilis, chlamydia)⁷
 - Alcohol use disorder⁷
 - Illicit non-injection drug use⁷
 - Injection drug use^{7, 14}
 - Black women¹⁴
 - Transgender women¹⁴
 - Men who have sex with men¹⁴
 - All individuals aged 18-24 yearsⁱⁱ¹⁴
 - Any history of PrEP use

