7.3. Variables

The following variables will be assessed at index date

- Demographic characteristics
 - Age (years)
 - Sex assigned at birth
 - Gender (trans, cis)
 - Race (African American/Black, Asian, White, Other Race)
 - Ethnicity (Hispanic, non-Hispanic)
 - Geographic Region (Northeast, Midwest, South, West, US Territories)
 - Marital status
 - Payer type (Medicaid, Medicare, Commercial insurance, Cash)
- Clinical characteristics
 - Time since first OPERA visit
 - Number of visits with OPERA healthcare provider (HCP) within 12 months prior to baseline
 - Prescriber specialty (MD or DO, physician associate, nurse practitioner, other/unknown)
 - Clinic type (healthcare center, wellness center, other)
- Sexual Behavior and Health
 - History of STI (ever)
 - a) Syphilis
 - b) Gonorrhea

ⁱ The CDC PrEP Clinical Practice Guideline recommends using an STI in the past 6 months as an indication for PrEP. This has been extended to an STI in the past 12 months for this protocol.

ⁱⁱ The National HIV/AIDS Strategy for the United States 2022–2025 identifies youth aged 12-24 as a priority population. This has been changed to individuals aged 18-24 in accordance with the study inclusion criteria Protocol for Non-Interventional Studies PASS Studies and Non-PASS Studies (4.0) March 2024

Template Doc ID: TMF-15706807

Parent Doc ID: VQD-SOP-066694

- c) Chlamydia
- d) Chancroid
- e) Lymphogranuloma venereum
- f) *Mycoplasma genitalium*
- g) Herpes Simplex-2 (HSV-2) infection
- h) Trichomoniasis infection
- i) Human papilloma virus (HPV)/genital warts
- o History of STI (past 3 months)
 - a) Syphilis
 - b) Gonorrhea
 - c) Chlamydia
 - d) Chancroid
 - e) Lymphogranuloma venereum
 - f) *Mycoplasma genitalium*
 - g) HSV-2
 - h) Trichomoniasis infection
 - i) HPV/genital warts

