- Coverage by LA PrEP will be determined based on the duration of medication from injection date forward. The number of days of coverage per injection were derived from the CAB LA PrEP USPI label.¹⁴
 - 1st injection: coverage = 37 days (30 days of coverage + 7-day injection window)
 - Subsequent injections: coverage = 67 days (60 days of coverage + 7-day injection window)
 - Each calendar day will only be counted once, even if there is an overlap between coverage from the prior injection and date of the next injection.

$$\% \text{ coverage} = \frac{\sum \min(\text{coverage, days between injections})}{\text{Number of FU days}} \times 100\%$$

HIV testing & STI screening

- HIV testing
 - Assessed within 14 days before PrEP start and over the first 12 months after PrEP start
 - Frequency and rate (per 100 person years) of HIV tests over 12-month period
 - Type of HIV tests (RNA [quantitative, qualitative], antigen/antibody, rapid screen)
 - Timing of HIV tests as recommended by PrEP clinical guidelines⁷
 - Oral PrEP: on-schedule testing defined as receiving an HIV test ≤14 days before/at start, and 3 months (76-104 days) after each test
 - LA PrEP: on-schedule testing defined as receiving an HIV test ≤14 days before/at first injection, and ±14 days of each subsequent injection
 - HIV testing practices (type, frequency) by type of healthcare provider (MD or DO, physician associate, nurse practitioner, other/unknown)
 - HIV testing practices (type, frequency) by clinic type (healthcare center, wellness center, other)
- STI screening
 - Assessed within 14 days before PrEP start and over the first 12 months after PrEP start
 - Frequency and rate (per 100 person years) of STI testing events (testing for multiple STIs on the same day will count as 1 testing event)
 - Type of other STI tests
 - Syphilis
 - Gonorrhea
 - Chlamydia
 - Chancroid
 - Lymphogranuloma venereum

- Mycoplasma genitalium
- Hepatitis B virus (HBV)
- Hepatitis C virus (HCV)
- HSV-2
- Trichomoniasis
- HPV and/or genital warts
- Timing of STI tests as recommended by PrEP clinical guidelines⁷
 - Testing 3 months (76-104 days) after last test
 - Testing 6 months (168-196 days) after last test
 - Testing 12 months (351-379 days) after last test
- STI screening practices (type, frequency) by type of healthcare provider (MD or DO, physician associate, nurse practitioner, other/unknown)
- STI screening practices (type, frequency) by clinic type (healthcare center, wellness center, other)

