7.9. Limitations of the research methods

CAB LA PrEP is directly observed; thus, injection records in the EHR provide certainty that PrEP was received and the exact timing of injections. However, oral PrEP use and timing cannot be ascertained with as much precision because only prescription records are available in the EHR. Incident HIV diagnosis can only be ascertained if tests are administered. Therefore, information on incident HIV diagnosis and exact timing may be subject to measurement error. Additionally, EHR data do not contain the following information to identify people who could benefit from PrEP: Other indications cannot be assessed in EHR data (HIV+ partner, ≥ 1 sex partner of unknown HIV status, inconsistent condom use, sex work)

Issues confronting population-level assessments include such aspects as differential medical care by practice size and specialty, academic and research orientation of the health care practitioner, ethnic-based & gender-based attitudes and geographic regional health care practices. OPERA clinical data is collected at point-of-care and is subject to the record-keeping practices of each healthcare provider and the standards of each clinic or organization. Patients may see multiple physician practices for various conditions, which may result in incomplete case ascertainment. Data is collected for the medical management of patients and is not directly intended for research purposes, but rather for the care and management of individual patients and patient populations.

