ANNEX 1 TABLES

Table shells for Analysis #1 are presented. Tables will be identical for Analysis #2, with the exception that study periods will be updated.

Table 1. Identification of the population of people without HIV in OPERA (Analysis #1)

	Included N (%)	Excluded N (%)
All individuals in OPERA		
≥1 clinical encounter between 01JAN2021 and 31DEC2021		
≥18 years old at first clinical encounter in 2021		
No evidence of HIV diagnosis before the first clinical encounter in 2021 [2021 pop]		
≥1 clinical encounter between 01JAN2022 and 31DEC2022		
≥18 years old at first clinical encounter in 2022		
No evidence of HIV diagnosis before the first clinical encounter in 2022 [2022 pop]		
≥1 clinical encounter between 01JAN2023 and 31DEC2023		
≥18 years old at first clinical encounter in 2023		
No evidence of HIV diagnosis before the first clinical encounter in 2023 [2023 pop]		

Table 2. Annual HIV incidence among people without HIV (Analysis #1)

	People without HIV, N	Incident HIV, ^a n (%)
2021		
2022		
2023		

^a New HIV diagnosis or positive HIV test (RNA, antigen/antibody)

Table 3. PrEP use among people with incident HIV (Analysis #1)

	People with incident HIV ^a N =
Never received PrEP, n (%)	
Ever received PrEP, n (%)	
Total number of days on PrEP, median (IQR) ^b	
Number of PrEP formulations received	
1, n (%)	
2, n (%)	
3, n (%)	
Any gaps between formulations, n (%) ^c	
Duration of gaps between formulations, median (IQR)	
PrEP use within ≤12 months before/on HIV diagnosis, n (%)	
Oral PrEP, n (%)	
TDF/FTC, n (%)	
TAF/FTC, n (%)	
CAB LA, n (%)	
Past PrEP use >12 months before HIV diagnosis, n (%)	
Oral PrEP, n (%)	
TDF/FTC, n (%)	
TAF/FTC, n (%)	
CAB LA, n (%)	

^a New HIV diagnosis or positive HIV test (RNA, antigen/antibody)

^b Including all formulations; gaps without PrEP do not count toward the total number of days on PrEP

^c Gap ≥31 days after oral PrEP, gap ≥37 days after first CAB LA injection, or gap ≥67 days after 2nd or subsequent CAB LA injection

Table 4. Identification of the PrEP users population

	Included N (%)	Excluded N (%)
All individuals in OPERA		
Ever received a PrEP prescription/injection in OPERA while HIV negative		
Start a new PrEP formulation (TDF/FTC, TAF/FTC, CAB LA) ^a between 21DEC2021 and 30JUN2023		
≥18 years old at start of index PrEP regimen		

^a Switch from one formulation to another or return to the same formulation after a pause ≥61 days without PrEP

Table 5. PrEP formulations used among PrEP users

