	PrEP users
PrEP formulation at index, N	
Oral, n (%)	
TDF/FTC, n (%)	
TAF/FTC, n (%)	
CAB LA, n (%)	
Switch from oral to CAB LA PrEP within 12 months of initiating index oral PrEP, n (%)	
Switch from CAB LA to oral PrEP within 12 months of initiating index CAB LA, n (%)	

Table 6. Demographic characteristics at start of PrEP regimen^a among PrEP users

	Oral PrEP N=	CAB LA PrEP N=
Age		
Median (IQR)		
18-29		
30-39		
40-49		
50-59		
≥60		
Sex		
Female		
Male		
Unknown		
Transgender, n (%) ^b		
Race		
Black		
Asian		
White		
Mixed or Other races		
Unknown race		
Hispanic ethnicity		
US Region		
Northeast		
South		
Midwest		
West		
US Territories		
Marital status		
Single		
Married/Domestic Partner		
Widowed		
Separated/divorced		
Unknown		
Payer ^c		
Medicaid		
Medicare		
Commercial Insurance		
Other		
Unknown		

^a Individuals who switched PrEP type during follow-up are included in both groups

^b Gender identity is not reported by all clinics and physicians; available data may be insufficient to infer cisgender identity.

^c Payer categories are not mutually exclusive.

Table 7. Clinical care characteristics at start of PrEP regimen^a among PrEP users

	Oral PrEP N=	CAB LA PrEP N=
Months since first OPERA visit, median (IQR)		
Any visits with OPERA provider within 12 months prior to start, n (%)		
Number of visits, median (IQR)		
Prescriber specialty, n (%)		
Infectious diseases		
General practice		
Other		
Unknown		
Clinic type, n (%)		
Healthcare center		
Wellness center		
Other		

^a Individuals who switched PrEP type during follow-up are included in both groups

Table 8. Sexual health characteristics at start of PrEP regimen^a among PrEP users

	Oral PrEP N=	CAB LA PrEP N=
History of STI (ever)		
Syphilis		
Gonorrhea		
Chlamydia		
Chancroid		
Lymphogranuloma venereum		
Mycoplasma genitalium		
Herpes Simplex-2		
Trichomoniasis		
Human papilloma virus/genital warts		
History of STI (past 3 months)		
Syphilis		
Gonorrhea		
Chlamydia		
Chancroid		
Lymphogranuloma venereum		
Mycoplasma genitalium		
Herpes Simplex-2		
Trichomoniasis		
Human papilloma virus/genital warts		

^a Individuals who switched PrEP type during follow-up are included in both groups

Table 9. Incident HIV^a within 12 months of index and through study end among PrEP users

	Oral PrEP N=	CAB LA PrEP N=
Within 12 months of index		
HIV diagnosis, n (%)		
Months from start of PrEP type to HIV diagnosis, median (IQR)		
Negative HIV test within 2 weeks before/on start of PrEP type, n (%)		

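### The 61-day PrEP-free gap that separates a start from continued use is applied without requiring any prior OPERA contact, so a person transferring in on the same formulation can be counted as a starter in Objectives 2-5

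*Protocol*

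**What the plan says.** Section 7.2.1 admits adults without HIV who started any new PrEP formulation in the inclusion window, with or without earlier PrEP. Criterion iv sets what counts as new: a different formulation, or "a gap ≥ 61 days without any PrEP immediately prior to the index PrEP". The footnote to Annex Table 4 repeats the rule: "Switch from one formulation to another or return to the same formulation after a pause ≥61 days without PrEP". The source of PrEP information appears in the same table, whose second row reads "Ever received a PrEP prescription/injection in OPERA while HIV negative".

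No row of Table 4 and no criterion in 7.2.1 asks for an OPERA contact before index. Prior contact appears only as description. Section 7.3 lists "Time since first OPERA visit" as a baseline variable, and Annex Table 7 has a row "Any visits with OPERA provider within 12 months prior to start, n" (%), which implies that people with no earlier visit can be included.

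For LA coverage, section 7.3.2 states: "1st injection: coverage = 37 days (30 days of coverage + 7-day injection window"). Later injections are credited 67 days (60 + 7).

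Section 7.9 acknowledges care elsewhere only in general terms: "Patients may see multiple physician practices for various conditions, which may result in incomplete case ascertainment". It does not mention earlier PrEP that OPERA cannot see.

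**The concern.** The purpose of criterion iv is to keep out continued use of the same formulation. It can do so only if the person was under observation during the 61 days. Without that, the first OPERA prescription or injection of someone continuing PrEP from an outside clinic satisfies criteria iii and iv.

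Several planned results treat that date as the true start:

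- **Index testing (Tables 14 and 20):** HIV test or STI screen in the 14 days up to and including the start.
- **Time to diagnosis (Table 9):** months from start of PrEP type to HIV diagnosis. For a transferred user the true start is earlier, so this is understated.
- **Attribution:** section 7.7.1.1 uses the timing of tests relative to PrEP start to judge whether an HIV acquisition is assigned to the correct PrEP type. A false start date weakens that check.
- **12-month HIV rate (Table 10):** affected if continuing users have a different risk from true starters.
- **CAB LA coverage (Table 12):** an injection from the middle of a series receives the first-injection credit.

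**Working it through.** **1. The plan's own count.** Section 7.5 gives first formulations of 12,110 (TAF/FTC), 9,740 (TDF/FTC) and 384 (CAB LA). Sum: 12,110 + 9,740 + 384 = 22,234, as stated. This confirms the addition but cannot show how many are true starts.

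**2. People misclassified, under assumption.** The documents give no transfer share f, so a range is assumed:

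| f (assumed) | 22,234 × f |
|---|---|
| 5% | 1,112 |
| 10% | 2,223 |
| 20% | 4,447 |
| 30% | 6,670 |

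**3. Effect on the 12-month HIV rate, under assumption.** Let r be the HIV rate in transferred users divided by the rate in true starters, and let f approximate their share of person-time. Then observed rate / true starters' rate = 1 − f + f × r.

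| f | r = 0.25 | r = 0.50 | r = 0.75 | r = 1.0 |
|---|---|---|---|---|
| 5% | 0.962 | 0.975 | 0.987 | 1.0 |
| 10% | 0.925 | 0.950 | 0.975 | 1.0 |
| 20% | 0.850 | 0.900 | 0.950 | 1.0 |
| 30% | 0.775 | 0.850 | 0.925 | 1.0 |

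Both f and r are assumptions. If r = 1 the rate does not change, but the time to diagnosis would still run from a false start.

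**4. CAB LA coverage for one transferred user.** Section 7.3.2 credits min(coverage, days between injections). Suppose the next injection comes 60 days after the first OPERA injection.

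- Treated as a first injection: min(37, 60) = 37 days.
- Treated as a later injection: min(67, 60) = 60 days.
- Loss: 60 − 37 = 23 days; 23/365 = 6.3 points of 12-month coverage.

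**5. Effect on mean CAB LA coverage.**

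- If 5% to 20% of all CAB LA users were transfers: 0.05 × 6.3 = 0.3 points to 0.20 × 6.3 = 1.3 points.
- People who switched to CAB LA later in the study period already had an oral index in OPERA and are at little risk of this error. Section 7.5 gives 384 with CAB LA at index and 292 later switchers. If the transfer share applies only to the 384, then 384/(384 + 292) = 57% of the effect remains: about 0.2 to 0.7 points. (The stated CAB LA total is 767 rather than 676, a separate discrepancy; on 767 the fraction is 50%, and the range is 0.2 to 0.6 points.)

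**The case against.** - **The cohort is not meant to be PrEP-naive.** This stands. Prior users are admitted openly and switchers need no gap. A reader might infer that continuing users in general contaminate the cohort. The documents do not support that: only people continuing the same formulation from outside OPERA are wrongly admitted.
- **Absence of records is not stated to mean absence of PrEP.** Criterion iv says without any PrEP, and section 7.4 describes complete patient health records, so outside PrEP noted at intake might be visible. The protocol does not say either way. The supportable claim is therefore that such people can be counted as starters, not that they all are.
- **The detail belongs in analysis specifications.** Section 7.8 does place population definitions there. But eligibility, the attrition table and the result shells are fixed in this protocol, and none includes an observation condition.
- **An index test may be due anyway.** Section 5 says testing is recommended before each oral refill and at each injection, so a continuing user may well have a test at the first OPERA record. This stands: the direction and size of any effect on index testing are unknown.
- **Table 7 already describes prior contact.** It gives the median and IQR of months since first visit and the share with any visit in the prior year. It does not show the share under 61 days or split any outcome by it.
- **CAB LA transfers were few at first.** Approval was on 20DEC2021 and inclusion opens the next day, so outside users could only accumulate during the window. This stands and limits the coverage effect.

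**Conclusion.** The gap holds on the text: criterion iv cannot be enforced for people not under OPERA observation in the 61 days before index, and nothing elsewhere in the protocol repairs it. Its size is unknown. The shares in the working are assumptions, and the documents supply no figure to replace them.

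Two stronger readings should be avoided.

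- Section 7.4 gives a mean follow-up of 1.2 years, and 61/(1.2 × 365.25) = 13.9%. A reader might infer that about 14% of starts are false. That figure assumes evenly spread starts and uses a mean for OPERA patients generally, not PrEP users. It counts people whose gap cannot be verified, many of whom are genuine starters who came to obtain PrEP.
- A reader might infer that well-timed CAB LA users would appear uncovered. A loss of 6.3 points leaves a fully covered user at about 94%, and the effect on the mean is likely about 1 point or less.

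The stronger case rests on the results dated from the start, especially time to HIV diagnosis and the attribution check. A prespecified sensitivity analysis is proportionate; excluding people is not.

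**What to change.** Keep the cohort as defined and make three changes.

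1. **Sections 7.2.1 and Annex Table 4:** add a flag for at least one OPERA contact between 12 months and 61 days before index. Apply it to people who qualify by the gap or by having no recorded prior PrEP. Switchers whose earlier PrEP is recorded in OPERA need no flag and stay in. The upper bound matters: without it, someone last seen years ago who returns already on PrEP would pass.
2. **Section 7.7.1.1:** prespecify a repeat of Tables 9, 10, 12 and 14 in the restricted set as a sensitivity analysis.
3. **Section 7.9:** state that PrEP received outside OPERA may be unseen, so unflagged starts are unverified. Do not relabel these people as non-initiators, since many will be genuine same-day starters.

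The cost is one flag derived from OPERA contact dates (time since first visit and prior-year visits are already planned) and four repeated tables. The restricted set will be smaller, especially for CAB LA. As an illustration with the plan's own formula at p = 0.5, the interval width is 2 × 1.96 × √(0.25/767) = 0.07 for all 767, and 2 × 1.96 × √(0.25/384) = 0.10 if half (384) remained. The set omits genuine same-day starters, and one contact does not prove continuous observation, so it shows whether results depend on unverified starts and should not replace the main analysis.
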